### Attachments

### Resources

Describe the availability of the resources and adequacy of the facilities that you will use to perform the research. Such resources may include:

- Staffing and personnel, in terms of availability, number, expertise, and experience;
- Computer or other technological resources, mobile or otherwise, required or created during the conduct of the research;
- Psychological, social, or medical services, including equipment needed to protect subjects, medical monitoring, ancillary care, or counseling or social support services that may be required because of research participation;
- Resources for communication with subjects, such as language translation/interpretation services.

The TMS Suite is housed within the department of psychiatry ([name]) at the University of Kentucky, Lexington. Currently it encompasses one experimental room covering about 600 sq feet on the second floor. We are in the process of purchasing a MagPro X100 stimulator (MagVenture Inc, Atlanta, GA) with booster option and active cooling. The room will also be equipped with a laptop and a chair to provide TMS. The device is capable of producing rTMS over a wide range of parameters such as paired-pulse, theta burst stimulation, and both monophasic and biphasic waveforms. The machine weighs 35 kg and the cart encompassing the machine weighs 16 kg. Dimensions of the machine are 210 x 530 x 400 mm. We are also in the process of purchasing a frameless stereotaxic system (Brainsight Frameless, Rogue Research, Montreal, QC, Canada) for co-

registration of TMS coil position on the scalp with underlying cortical anatomy on the individual subject's three-dimensionally rendered MRI scan. This permits navigation of the TMS coil to target cortical structures. Participants are administered TMS in a customized chair for stabilization of head and coil position. A coil holder especially designed for TMS ensures stable coil positioning. The Brainsight Neuronavigation system has three main components: (1) NDI Spectra infrared camera system, (2) stimulator, (3) chair with neck rest. The TMS coil is targeted to a user defined location selected on the individual 3-D Anatomical MRI with fMRI or PET data overlay with less than one millimeter error. The TMS coil is attached to a stimulator unit, which administers the TMS pulses to modulate brain function in a spatially and temporally precise fashion. The subject reclines in the chair and wears a headband equipped with a subject position tracker. The ceiling mounted infrared stereo camera detects the 3-D position of the subject tracker and also the coil position tracker, and continuously feeds this information into the control center software.

**Eye Tracker.** The Tobii Pro Fusion housed at [name] is an exceptionally flexible remote eye tracking system offering supreme tracking performance in a wide array of human behavior research studies. This small eye tracking research system offers unprecedented portability and freedom of head movement in combination with unparalleled tracking accuracy and robust participant tracking capability. It allows for both screen and real-world test scenarios. For screen based research, it can be used with a laptop, an external monitor or an all-in-one PC. It can be mounted below most screens. With the eye tracker flush mounted on a screen, researchers can achieve highly accurate results for stimuli presentation on screens. Using a desk stand, one can track larger screens. This gives researchers the freedom to present stimuli on a screen that best meets the specific needs of the study at hand. The eye tracking system captures data up to speeds of 250 Hz (available 60, 120, 250 Hz modes). It delivers unparalleled data accuracy within the whole tracking box and very robust participant tracking capability. Robust eye tracking capability ensures very low data loss in real life conditions. The system with automatic selection of bright or dark pupil eye tracking accommodates for large variations in experimental conditions and demographic populations. The system also comes fitted with Tobii Pro Lab. This is a versatile biometric software platform designed for extensive research into human behavior using eye tracking analysis. It also has added ability to be combined with other physiological data streams. From in-store shopper research to psychology experiments, Pro Lab makes it easy for anyone to start using various biometric tools in their research in order to further expand the scope and richness of their insights. Pro Lab works well with both screen-based and wearable eye trackers.

**Magnetic Resonance Imaging and Spectroscopy Center (MRISC).** The Magnetic Resonance Imaging and Spectroscopy Center (MRISC) is a service and consultation center supporting basic and clinical research at the University of Kentucky. The Center includes an advanced 3T Siemens PRISMA scanner with high performance gradients, echo-planar whole body imaging and hydrogen spectroscopic capabilities for both human and animal studies. For dedicated animal studies, a modern Bruker/Siemens 7T MR scanner has recently been installed. Recently renovated facilities for animal handling, preparation and care are available immediately adjacent to the 7T imager. There are also computing facilities, electronic and fabrication shops, and a multi-user laboratory available to support magnetic resonance and spectroscopy studies. Scientific and technical personnel are available to help in developing MR sequences and procedures as well as to help with image-processing analysis. The Center has multiple ongoing research trials <https://www.research.uky.edu/magnetic-resonance-imaging-and-spectroscopy-center/human-research-projects>.

In 2017 the MRISC was awarded an NIH grant to upgrade its human MRI scanner from a Siemens TIM TRIO 3T to a Siemens MAGNETOM Prisma 3T. The Prisma 3T offers maximum performance under prolonged high-strain conditions and delivers improved resolution over the previous system by coils with the highest gradient strength currently available on the market. Of note, data collected with the Prisma 3T scanner are to a higher-quality standard and are therefore more attractive for inclusion into NIH-supported neuroimaging repositories, such as the Neuroimaging Informatics Tools and Resources Clearinghouse (NITRC) and the Human Connectome Project (HCP). The Prisma 3T is equipped with a full complement of coils, updated image processing using Siemens Software 3D rendering, image fusion, perfusion, DTI fiber tracking, spectroscopy, volume rendering, shaded surface display, multiplanar reconstruction, and maximum intensity projection.

**Ancillary Equipment in MRI Suite.** 1) Applied Sciences Laboratories, Inc. Model 504LRO (long range optics) eye tracker complete with Real Eye software; 2) AVOTEC, Inc. Silent Vision SL-6011 LCD projection system used with Psychology Software Tools, Inc. visual presentation software, EPRIME; 3) MRA, Inc. 10 channel, fiber optic, patient response system with trigger interface and visual/auditory patient monitoring; 4) Current Designs, Inc. patient response fORP Interface Unit with 12 fiber optic cables and an MRI compatible, handheld, trackball mouse; 5) Medrad, Inc. SHS200 Power Injector; 6) InVivo Research, Inc. Precess MRI compatible patient monitor with wireless digital SPO2, ETCO2, heart rate and blood pressure recording; 7) Full suite of physiological monitoring equipment from S.A. INC for small animal imaging; and 8) Microcapstar Capnograph CO2 Analyzer and MRI-1ventilator from CWE instruments for small and medium sized animals.

**Computing and Data Management.** The following centralized computer and file server equipment is located in the MRISC and available (1) Server, Linux, 4U Rack mounted Dell PowerEdge 6850, 64bit - 4 Quad Core Xeon Tulsa, 16GB RAM, 1.5TB SAS RAID 5 array; (2) Two Disk Array, 3U Rack mounted Dell MD1000 Power Vault, 4.5TB SAS RAID 5 array; (3) Tape Backup, 2U Rack mounted Dell TL2000, 24 x 800GB/1.6TB cartridges; (4) Network Attached Storage (NAS), 1U Rack mounted NetGear, 2.0 TB SATA RAID 5 array; (5) Dell full size 4210 rack (42U slots total; 16U slots occupied including APC; 26U slots available).

All computers and servers are protected with power supply backup and surge protecting UPSs. All MRI scans are sent to the NAS backup server immediately after the imaging session and burned to CD for permanent archiving. The MRI scanner host computer is connected to the Dell rack, containing equipment items 1-4, by 1 GB/sec fiber optic cable while the rest of the computers are connected by Cat 5e cable on a 100 MB/sec network. Institution-wide upgrades to Cat 6a network cable are currently underway. Daily incremental tape backups are made from all data on all the servers, the NAS, and the MD1000 using Yosemite Backup software running on the Poweredge 6850. Full monthly tape backups are made and stored offsite. All computers and servers are behind the UK Medical Center firewall, have individual firewalls, are accessible only with valid usernames and passwords, and have automated operating system software updating.

**Bluegrass Care Clinic for HIV.** The Bluegrass Care Clinic, located in Lexington, Kentucky provides HIV care, case management and psychiatric services for PLWHA in the north central Kentucky region. Currently, the clinic provides care to 1700 unique PLWHA. Approximately 175 new unique clients enroll in the clinic each year. Seventy percent of people receiving care at the Bluegrass Clinic self-report smoking cigarettes, 97% receive a prescription for anti-retroviral medication and 93% remain virally suppressed. In the

Bluegrass Care Clinic there are approximately 1073 unique PLWHA, engaged in care who smoke. If we conservatively assume 1/2 may be ineligible for the study or chose not participate in the study, there are still over 500 eligible people to recruit for the study. This is nearly 2.5 times the number of people we would need to recruit (n=240) over the course of five years of the grant, if funded. These patients identify as male (81%), (18%) and transgender (1%).

The Supportive Medication Assisted Recovery Program (SMART) aims to comprehensively assess evaluation and treatment needs of patients with substance use disorders. It is housed at [name] and associated with the University of Kentucky. This clinic provides pharmacotherapy and psychotherapy treatment options for these patients in addition to urine drug screens and breathalyzer tests. Having 2 full time psychiatrists, 1 psychologists and 2 social workers on all days of the week, the clinic seeks to become a leader in integrative care in the state of Kentucky.

## Potential Risks & Benefits

### Risks

- Describe any potential risks – including physical, psychological, social, legal, ability to re-identify subjects, or other risks. Assess the seriousness and likelihood of each risk.
- Which risks may affect a subject's willingness to participate in the study?
- Describe likely adverse effects of drugs, biologics, devices or procedures participants may encounter while in the study.
- *Qualitative research* - describe ethical issues that could arise while conducting research in the field and strategies you may use to handle those situations.
- Describe any steps to mitigate these risks.

### Benefits

- Describe potential direct benefits to study participants – including diagnostic or therapeutic, physical, psychological or emotional, learning benefits. This cannot include incentives or payments.
- State if there are no direct benefits.
- Describe potential benefits to society and/or general knowledge to be gained.

Describe why potential benefits are reasonable in relation to potential risks. If applicable, justify why risks to vulnerable subjects are reasonable to potential benefits.

Seizure is a theoretical risk with TMS. In the Rossi et al. report it was stated that "The occurrence of seizures has been extremely rare, with most of the few new cases receiving rTMS protocols exceeding previous guidelines, often in patients under treatment with drugs which potentially lowered the seizure threshold." As Rossi et al. delineate, "rare" means that 16 cases (out of tens of thousands of rTMS sessions over the last two decades) of seizure related to rTMS have been reported. Eight occurred before safety parameters were established in 1997. Of the other eight reports, six occurred either when the safe rTMS parameters were exceeded or other safety guidelines ignored, and the actual occurrence of a seizure has been questioned in the other two (i.e., convulsive syncope or pseudoseizure may have occurred). In a workshop convened by the National Institute for Neurological Disorders and Stroke (NINDS) in 1996, researchers in the field agreed upon a set of rTMS consensus safety guidelines, including recommended stimulation parameters and contra-indications, and these consensus guidelines have been recently updated (Rossi et al., 2009). Widespread adherence to the 1996 guidelines has resulted in the virtual elimination of inadvertent seizures in rTMS studies (Rossi et al., 2009). Theta burst stimulation (TBS) that we will use in this study has been documented to be extremely safe. The risk of seizure with TBS is 0.1% (Rachid, 2017). There has been only one seizure instance reported with continuous TBS in a subject with no previous history of epilepsy but was sleep deprived after a long flight (Oberman and Pascual-Leone, 2009).

The most commonly reported side effect of rTMS is headache. This headache is typically of a muscle-tension type. It usually develops during or immediately after the stimulation and may last for minutes to hours following the end of the stimulation. It is typically limited to the day of stimulation, and usually responds promptly to single doses of over the counter pain medications. Neck pain or scalp pain may also occur. Both are usually managed easily with over-the-counter analgesics.

As noted in Rossi et al. (2009), Loo and colleagues reported mild and transient changes in auditory threshold in two depressed patients following a 2-4 week rTMS course of rTMS (16). Cases of tinnitus have been reported after rTMS treatments. In addition, recently in a study investigating the effects of rTMS on symptoms of depression, a patient experienced moderate to severe tinnitus after an rTMS session in which earplugs were not used. Rossi et al. recommended that hearing protection always should be worn during rTMS application, and that individuals with cochlear implants not receive rTMS. In the current study, earplugs will be worn by all subjects during rTMS procedures. Individuals with cochlear implants will be excluded from participation.

Risks to the unborn children of pregnant women receiving rTMS are unknown. Pregnant women will be excluded in this study. If sexually active, the subject must agree to use appropriate contraceptive measures for the duration of the study. Medically acceptable contraceptives include: (1) surgical sterilization (such as a tubal ligation or hysterectomy), (2) approved hormonal contraceptives (such as birth control pills, patches, implants or injections), (3) barrier methods (such as a condom or diaphragm) used with spermicide, or (4) an intrauterine device (IUD). Contraceptive measures such as Plan B (TM), sold for emergency use after unprotected sex, are not acceptable methods for routine use. If the subject has any uncertainty about whether they could be pregnant, another urine pregnancy test will be performed before they can participate in this protocol.

The EKG leads can cause an allergic reaction causing your skin to become red at its point of contact with your wrist. We will remove the leads if you develop itching or skin redness at the site of application. The possible risks associated with blood drawing are pain, bleeding, fainting, bruising, infection and/or hematoma (blood clot under the skin) at the injection site. Since the blood draws will occur

at the CCTS outpatient clinic at PAV H of A.B. Chandler Hospital, we can avail specialized services if needed.

Other plausible risks include breach of confidentiality, development of suicidal thoughts and syncope (neurocardiogenic in nature). Vasodepressor (neurocardiogenic) syncope is a common reaction to anxiety and psycho-physical discomfort. It is a common experience that may occur more often than epileptic seizures during TMS testing and treatment. Suicidal thoughts have been observed to transiently develop only in subjects who have a previous history of major depressive disorder.

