On day one of the study, following informed consent, we will perform baseline assessments including breath alcohol level, opioid and tobacco craving questionnaires, smoking attentional bias tasks using eye tracker, inhibitory control and delay discounting tasks, collection of baseline demographics, vital signs (including heart rate, systolic and diastolic blood pressures), Snaith Hamilton Pleasure Scale and Hamilton depression rating scale. All of these baseline assessments will take a total of three hours. We will also obtain resting and active motor threshold from the first dorsal interosseous (FDI) muscle. Following this subjects will be transported to Magnetic Resonance Imaging and Spectroscopy Center (MRISC), affiliated with University of Kentucky for collection of their baseline MRI brain scan that will last thirty minutes. Subjects will also be escorted to the MRISC at the UK Medical Center by the PI ([name]) and a research assistant. Subsequently, neuroimaging data (MRI brain) will be acquired using a Siemens 3-Tesla (3T) PRISMA MRI scanner as described under Data Collection below. On the second and third days, subjects will receive either four sessions of active TBS or four sessions of sham stimulation. Subjects will receive all four sessions of either TBS or sham on one particular day, all four sessions will be the same in dosing and will be delivered at an interval of fifty minutes each. Each session will last ten minutes regardless of it being TBS or sham. Sessions will be delivered 120% resting motor threshold (RMT) to the left dorsolateral prefrontal cortex using a figure 8 coil and MagVenture MagPro x100 device (MagVenture A/S, Denmark), with TMS coil position stabilized using BrainSight (Rogue Solutions, Montreal, Canada). Deciding who will get TBS/sham sessions on day two will be done in a randomized manner with counterbalancing. Along with the stimulation, subjects will also perform a host of other tasks as shown in figures 1. Craving for cigarettes will be measured while performing a stress induction procedure involving immersion of feet in cold water coupled with performing a working memory task (cold pressor test and PASAT as described below). The figures also indicate the timing of these tasks. At the end of the stimulation sessions and tasks, post session MRI brain scans will be collected and subjects will be dispersed payments for the respective days.

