#### Modification Request to the research procedures:

An additional two follow-up visits will be added to this study research procedure by the study Principal Investigator [name]. [name]. The research team will follow up with subjects at one-week and two-week intervals with a urine cotinine test (ACCUTEST urine cotinine tests from Janet Pharmacocal) and carbon monoxide testing using Smokerlyzer (Bedfont Scientific Limited). These two follow-up short visits 2-3 minutes will be performed in the SMART clinic lab space. The CUTEST cotinine assay is a qualitative test and indicates the presence or absence of cotinine. Cotinine is a metabolite of nicotine, and these measures will help assess abstinence from cigarette smoking in response to our intervention. The additional follow-up visit details will be incorporated into the informed consent form and in the E-IRB application for IRB further review and approval.

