Should a participant voice suicidal ideation at any point during the study, a thorough risk assessment would be completed immediately and the appropriate resources would be contacted including emergency and/or outpatient resources. To mitigate risk of breach of confidentiality or invasion of privacy, all procedures as part of the study will be completed at [name] offices. Participant personal information and medical/psychiatric history will be stored on the University of Kentucky building at [name]. Also, in order to mitigate risk of breach of confidentiality or invasion of privacy, HIPAA will be discussed with each participant at each session.

The main risks with TMS include seizures. We will screen subjects for known risk factors for seizure with rTMS (medical screening and medical history). Personnel who administer rTMS are trained to recognize a potential seizure event and to act as "first responders" to administer appropriate initial care. All study personnel will undergo basic life skills (BLS) training, and seizure-specific training. The major physical signs the study personnel will look out for in detecting a potential seizure include chewing movements, convulsions/tremor/shaking, difficulty talking, a blank stare, eyes rolling up, and profuse sweating. If any of these signs are observed, study personnel will stop the research procedure and inquire whether the subject feels okay. If the subject is unresponsive (and therefore likely experiencing a seizure), first-aid will be supplied. The first-aid response consists of making sure the subject is physically safe for the duration of the seizure. This involves moving the subjects out of the TMS chair and onto the floor lying down on his or her left side. The subject will be kept lying down on his or her left side, while the staff call emergency medical help, via a 911 call. Resources available in the laboratory include a first-aid kit and immediate phone access. A seizure constitutes a reportable adverse event, and will thus be immediately reported to the IRB via the Safety Events Form mechanism.

Initial measures for syncope are identical to those for seizures. TMS will be terminated immediately, and the subject assisted in controlled reclining without impact. Airway breathing and circulation will be assessed. Unless tonic-clonic seizure activity occurs, the subject will be turned on one side to help clear the airway and avoid aspiration.

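### Suicidal thoughts are a named risk, but the visible text schedules no mood or suicidality question after stimulation and no harm assessment at the one- and two-week visits

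*Combined protocol and SAP*

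**What the plan says.** All references are to the combined protocol and SAP.

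- **Named risks (Potential Risks & Benefits).** Headache: "The most commonly reported side effect of rTMS is headache"; of its time course the plan says "It is typically limited to the day of stimulation". Tinnitus: "Cases of tinnitus have been reported after rTMS treatments". Suicidal thoughts are listed among the other plausible risks, with the group concerned identified: "Suicidal thoughts have been observed to transiently develop only in subjects who have a previous history of major depressive disorder".
- **Eligibility (Subject Demographics).** Schizophrenia, seizure disorder and traumatic brain injury are excluded. A history of major depression is not on the list.
- **Depression rating (Study Design; Research Procedures).** The day-one baseline list ends with the "Snaith Hamilton Pleasure Scale and Hamilton depression rating scale". No later administration is described in the text.
- **Follow-up visits (Modification Request to the research procedures; repeated under Data Collection & Research Materials).** Two visits, at one and two weeks, take urine cotinine and exhaled CO to assess abstinence. Their length and place are given: "These two follow-up short visits 2-3 minutes will be performed in the SMART clinic lab space".
- **Trigger for a suicide-risk assessment (Records, Privacy, and Confidentiality, under Digital Data).** The assessment follows "Should a participant voice suicidal ideation at any point during the study".
- **Side-effect instrument.** A TMS side-effects scale is listed under Data Collection & Research Materials, and the form is attached under Research Procedures. The text gives neither its items nor its timing.

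**The concern.** The plan names a psychiatric harm, names the people in whom it has been seen, can enrol those people, and measures depression once, before exposure. A single pre-treatment score cannot show emergent change. If nobody asks afterwards, a participant who develops suicidal thoughts some days after stimulation could attend both follow-up visits without being asked about them. The same holds for tinnitus that starts late or persists.

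Two things are at stake. One is participant safety: the risk assessment that the plan already describes is reached only if the participant speaks first. The other is interpretation: a report of no such events would not distinguish between no events and no questions. This matters beyond the pilot, because the Background section says its data will support a resubmitted grant application.

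**Working it through.** No arithmetic applies; the point concerns when and how harms are asked about. The check sets the risk, procedure, follow-up and safety sections side by side.

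**Step 1. What is solicited after stimulation, harm by harm, in the visible text**

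| Harm | Course stated in the plan | Stimulation day | One- and two-week visits |
|---|---|---|---|
| Headache | During or soon after stimulation, usually that day only | Side-effects scale possible; timing not given | None described |
| Tinnitus | Reported after treatment; no time course | Side-effects scale possible; items not visible | None described |
| Suicidal thoughts | Transient, with prior major depression; onset not given | No question described | None described |

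**Step 2. Is there another rating that could show emergent mood change?** The day-two description in Study Design covers craving scales, a visual attention task, the cold-water stress task and an MRI scan. The later modification adds heart-rate recordings on day two and C-reactive protein on days one and two. None of these asks about mood or suicidality. The Hamilton scale stands only in the day-one list, which appears in both Study Design and Research Procedures.

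**Step 3. Could the follow-up visits hold such a question?** Their content is stated twice and their length once. A contact of 2-3 minutes with a urine test and a breath test leaves little room for a full rating, although a brief question or form would be possible. None is described.

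**Step 4. What remains after the participant leaves?** The same section on records and privacy tells participants who are hurt or sick to call, with an after-hours number. Data and Safety Monitoring promises procedures for detecting harm promptly, but gives no instrument and no schedule. The call route depends on the participant; the general promise cannot be checked.

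**Step 5. Count.** In the visible text there are two in-person contacts after stimulation and no scheduled suicidality, mood or adverse-event question at either. The text does not say from which day the one and two weeks are counted, so the exact length of the unasked window is not known.

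**The case against.** The strongest answer has four parts.

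1. **The plan does solicit side effects.** The TMS side-effects scale is a listed and attached instrument. A reader might infer from the sections above that every harm after stimulation is caught only if a participant volunteers it. The documents do not support that. The scale may well capture headache and tinnitus on the stimulation day, staff are trained to watch for seizure signs, and the investigator, a psychiatrist, supervises the TMS session. This part stands, and it limits the point to suicidal thoughts and to harms that arise or persist after that day.
2. **The schedule sits in a figure that is not shown.** Research Procedures refers task timing to figures, and Figure 1 is titled as covering all four visits. Its absence here is not a defect, and it may schedule the scale or a repeat Hamilton rating. A reader might also infer that participants are certainly never asked; that cannot be shown. The conclusion must stay conditional. If the figure does schedule such a question, the written description of the visits should be reconciled with it.
3. **The harms are minor or already handled.** Headache is mostly a same-day event, so follow-up questions add little. The tinnitus case described in most detail followed a session without earplugs, and all participants here wear them. Psychiatric comorbidity is already among the stored participant data, so it would be wrong to say that the plan fails to record history; only its use to identify the named group is missing. All this is fair, but none of it supplies a question about suicidal thoughts after stimulation.
4. **Enrolment is closed.** The continuation review reports 4 participants enrolled and data under analysis. An amendment cannot create data for anyone who has finished follow-up. This stands, and it divides the fix into reporting now and assessment for any further participants.

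**Conclusion.** The point holds in a limited form. The plan names treatment-emergent suicidal thoughts as a plausible risk in people it does not exclude. Its visible text has one depression rating, before stimulation, and no scheduled suicidality or harm question at either of two later visits. Suicidal thoughts above all, and other harms that arise or persist after the stimulation day, therefore appear to depend on spontaneous report.

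This rests on two assumptions: that Figure 1 does not schedule a mood, suicidality or side-effect assessment after stimulation, and that the side-effects form is not used at follow-up. Both can be settled by reading the attachments.

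The change is worthwhile for safety and inexpensive. It does not affect the comparison of attentional bias and craving stated under Objectives. Nothing here implies that the eligibility criteria are wrong; the point concerns only what is asked of those who enrol.

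**What to change.** **For any further participants, and for a successor trial:**

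- In the modification describing the one- and two-week visits, and in its repeat under Data Collection & Research Materials, add the existing TMS side-effects scale and one direct suicidality question. The suicide item of the Hamilton scale would serve, assuming the standard version is in use.
- Ask the same question after the last session of each stimulation day, if Figure 1 does not already do so. State in the text when the side-effects scale is given.
- Use the psychiatric history already recorded to identify participants with previous major depression.
- Send any positive answer to the risk assessment already described under Digital Data.

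**For participants who have completed follow-up:** state when the side-effects scale was given and what it covers. If harms after the stimulation day were not solicited, say so, and do not present an absence of such events as evidence of tolerability.

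**Cost:** a short amendment and a few more minutes per visit, using instruments already in the study. The stated 2-3 minute visit length would need to be revised.
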